5.4 Schedule Modifications

Modifications of dose or administration interval will not be allowed.

5.5 Concomitant Medication

The following medication is not allowed while the patient is included in the study:

- NSAID
- Corticosteroids
- Other anti-inflammatory pharmaceutical substances.
- Antibiotics
- Probiotic formulas other than the Investigational Product.

All concomitant medication (incl. herbal preparation and other “over-the-counter” drugs) used by the patient will be recorded in the patient’s file and Case Record Form (CRF).

5.5.1 Non-investigational products

All subjects included will at screening be dispensed one packet of two sachets of Citrafleet® (ATC code: A06A B58) for bowel emptying. The participating subjects will be instructed to take the servings prior to the colonoscopy according to written information conveyed at screening visit.

5.6 Subject Compliance

Compliance will be calculated based on the number of returned capsules and the number of planned days with the interventional product.

5.7 Investigational Product Accountability

The PI will confirm receipt of study product and will use the study product only within the framework of this clinical study and in accordance with this protocol. Receipt, distribution, return, and destruction (if any) of the study product must be properly documented according to the sponsor’s agreed and specified procedures.

The study product will be ordered from importer/distributor by the study pharmacist. Labeling and dispensation will be performed by the PI in collaboration of the study pharmacist. Study pharmacist will be responsible for product receipt. Unused returned capsules will be destroyed by the pharmacist.

All investigational product containers (opened, unopened, or empty) must be returned to the sponsor after the study. An investigational product dispensing log must be prepared for each subject. At weeks 0 and 8 and at any other relevant time point the following information must be entered into the investigational product dispensing log:

- Date of visit

- Number of containers given to the patient, including individual container batch number(s)
- Number of containers returned from the patient, including individual container number(s) and whether they are unopened, opened or empty
- The number of capsules left in the containers which are opened, but not empty
- Explanation of any discrepancies
- Signature of the person distributing/collecting the container(s)

After completion of the study, the completed investigational product dispensing logs must be signed by the investigator

5.8 Product Labeling

The investigational product will have a label permanently affixed to the container outside and will be labeled according to standards originally designed for medicinal products such as ICH GCP.

In addition to manufacturer information (i.e. batch id, expiration date) labels will state (in Norwegian):

TIL UTPRØVING

Studiepasient (initialer og inklusjonsnummer): (fylles ut)

IDOFORM®Travel kapsler

4 kapsler en gang daglig (Tas sammen med andre medisiner).

Oppbevares i romtemperatur utilgjengelig for barn

Oslo universitetssykehus HF, [name]

Studiekode: OUSHIVProbiot2

Kontaktperson: [name], Infeksjonsmedisinsk avdeling,
Telefon [name] / [name]. Ta kontakt i nødstilfelle for informasjon
om IDOFORM®Travel og studien.

TA MED PAKNINGEN VED NESTE KONTROLL. IKKE KAST TOMME PAKNINGER

5.9 Subject Numbering

Each subject is identified in the study by a unique subject number that is assigned when subject signs the Informed Consent Form. Once assigned the subject number cannot be reused for any other subject

The study treatment will be administered to the subject by the investigators only.

6 STUDY PROCEDURES

6.1 Flow Chart

	Screening period	Baseline	Treatment period ¹⁾					Follow up ¹⁾
Week	-4 to -1	0 Product start	1 ²⁾	3 ²⁾	5 ²⁾	7 ²⁾	8 Product stop	10 ²⁾
Informed consent	X							
Inclusion/exclusion Evaluation	X	X						
Medical history and Clinical status	X	X						
Concom. med.	X	X	X	X	X	X	X	
Vital signs		X					X	
Physical exam		X					x	
Clinical chemistry	X	X					X	
Biological markers	X	X					X	
Product dispensing		X						
Product collecting							X	
Adverse events		X	X	X	X	X	X	x
Colonoscopy/Stool sample		X					X	

¹⁾INR patients/intervention study only. ²⁾ Telephone interview.

6.2 By Visit

Informed consent:

Informed consent must have been given by each subject before any study specific procedures are initiated, preferably at screening visit. The following tests will be done at screening:

Clinical status and Vital signs:

Medical history (including disease history and corresponding treatment details), physical examination (eg. cor/pulm/abdomen and peripheral lymph node status), and vital signs (weight, blood pressure, temperature and pulse).

Before vital signs are measured, the subject should be resting seated for at least 2 minutes. Any vital sign value after start of treatment that is judged by the investigator as a clinically significant worsening compared to previous exam will be considered an adverse event (AE), documented on the subject's CRF, and followed until the outcome is determined.

Concomitant medication:

All concomitant medication (incl. herbal preparation and other “over-the-counter” drugs) used by the subject within 28 days of treatment start must be recorded in the CRF. Check boxes in CRF for NSAID, glucocorticoids, disease-modifying antirheumatic drugs, and other anti-inflammatory drugs, antithrombotic drugs, antibiotics (within 3 months) and probiotics (within 3 months)

Clinical chemistry and Biological markers:

Blood samples will be taken to determine clinical chemistry analyses and biological markers.

Clinical chemistry include (one 4 ml sample tube of EDTA whole blood and one 5 ml sample Serum Separation Tube): hemoglobin, white blood cells differential count, thrombocytes, mean corpuscular hemoglobin, mean corpuscular volume, HbA1c, vitamin B12, folate, bilirubin, uric acid, C-reactive protein (CRP), sodium, potassium, creatinine, aspartate aminotransferase, alanine aminotransferase (ALAT), gamma-glutamyl transferase, lactate dehydrogenase, alkaline phosphatase, albumin, amylase, creatin kinase (CK), and lipid profile.

Biological markers include (one 2,5 ml sample tube of EDTA whole blood and one 5 ml sample Plasma Preparation Tube): CD4+ and CD8+ T cell counts and HIV RNA quantification.

In addition the following material will be collected from included subjects for exploratory assays and analyses: One 4 ml sample tube of EDTA whole blood, one 3.5 ml sample Citrate-Na tube, one 5 ml sample of Plasma Preparation Tube (CPT), and one 5 ml sample Serum Separation Tube and eight 7 ml samples Cell Preparation Tubes.

Adverse events:

See section 8.

Colonoscopy:

Included subjects will perform bowel emptying procedure with Citrafleet® (see also section 5.5.1) starting 20-28 hours in advance of colonoscopy.

Peripheral vein cannula will be inserted in case of peri-procedural need for sedation with midazolam 5-10 mg intravenously according to routine colonoscopy procedures.

Full endoscopic examination will be performed from rectum to terminal ileum. Subsequently, multiple biopsies will be collected in terminal ileum, ascending colon and sigmoid colon will be collected. See section 6.5.3 for further details.

A Standard Operating Procedure (SOP) for the colonoscopy will be produced in Norwegian to ascertain a safe, uniform and reproducible procedure in all study subjects.

Stool samples

Included subjects will immediately before starting bowel emptying sample a tea-spoon size of own stool that they will bring to the upcoming visit and colonoscopy. All included subjects will at screening visit be given a sampling kit for the collection of the stool samples.

6.2.1 Before Treatment Starts

Tentative participants (cases and controls) will be invited by letter or telephone call to participate. Screening visit agreed upon by telephone. Alternatively, tentative participants invited at routine checkup at the outpatient clinic at Dep. of Infectious Diseases at Oslo University Hospital (OUH).

Screening visit agenda:

- Recording medical history including medication
- Clinical examination
- Blood samples (se section 6.2)
- Evaluation of eligibility based on inclusion and exclusion criteria.
- Oral and written information about the treatment, colonoscopic procedure and follow up.
- If eligible and accepting participation, subjects signs informed consent. (See appendix for patient information and informed consent form).
- Information about preparations to colonoscopy and dispensing of Citrafleet® for pre-procedure bowel emptying.

6.2.2 During Treatment

Week 0: Inclusion. First visit at the endoscopy unit at outpatient clinic at Dep. of Gastroenterology, OUH.

First visit/colonoscopy agenda:

- Review of medical history
- Clinical examination
- Vital signs
- Blood samples (se section 6.2)
- Colonoscopy with biopsy collection according to SOP.
- Dispensing of study treatment (IDOFORM®Travel) for eight weeks consumption.

Week 1-7: Bi-weekly telephone interviews. Record adverse events and update concomitant medication. In case of serious adverse events or side effects, arrangement of subject visit at outpatient clinic at Dep. of Infectious Diseases

6.2.3 End of Study Visit

Week 8: End of study visit and colonoscopy at Dep. of Gastroenterology, OUH.

End of study visit/colonoscopy agenda:

- Adverse events
- Clinical examination
- Vital signs
- Blood samples (see section 6.2)
- Colonoscopy with biopsies collection according to SOP.
- Collection of residual interventional product packages and residual capsules.

6.2.4 Withdrawal Visit

Should a subject wish to withdraw (see also section 6.3) a visit for complete final evaluation at the time of the subject's withdrawal will be arranged.

A withdrawal visit will record the reason, date, and time for withdrawal in the CRF and include clinical examination and vital signs. If possible, measurements and recordings should continue according to the protocol.

The specific event or test result(s) being the reason for withdrawal will be recorded in the CRF.

6.2.5 After End of Treatment (Follow-up)

Week 12: Telephone interview recording adverse events. In case of serious adverse events or side effects, arrangement of a visit at the outpatient clinic at Dep. of Infectious Diseases will be made.

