Investigational product (including active comparator and placebo) :	IDOFORM®Travel No placebo/active comparator
Centers:	Oslo University Hospital (single center)
Study Period:	Estimated date of first patient enrolled: 01.12.2015 Anticipated recruitment period: 18 months Estimated date of last patient completed: 30.11.2017
Treatment Duration:	8 weeks
Follow-up:	One follow-up consultation 2 weeks after completed therapy
Objectives	Primary: Assess the safety of a probiotic compound (IDOFORM®Travel) in combined anti-retroviral therapy (cART)-treated immunologic non-responder (INR) patients with chronic HIV infection. Secondary: i) Explore the biological effects of probiotics in cART-treated INR patient with chronic HIV infection; and ii) investigate differences between cART-treated HIV-infected INR and non-INR patients with regards to gut microbiome and mucosal barrier function.
Endpoints:	Primary endpoints: i) Adverse effects; ii) Δ plasma viral load; and iii) Δ blood CD4 count. Secondary/Exploratory endpoints: Alterations in i) Gut microbiota composition; ii) Gene expression of gut epithelial cells; iii) Frequency and activation status of CD4+ T cell subsets in gut lamina propria, including Th17 and Th22 subsets; iv) Frequency, activation status and intracellular signaling of systemic T cells; and v) Soluble

	systemic markers of chronic inflammation and immune activation.
Study Design:	
 1) Single arm, open label, consecutive case series, single center intervention study on cART-treated INR patients with chronic HIV infection 2) Subsidiary cross-sectional case control, single center study comparing cART-treated INR patients with chronic HIV infection to non-INR patients with chronic HIV infection and to healthy controls.

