3 OVERALL STUDY DESIGN

[figure not shown]
The primary study is a phase I, single arm, open label, consecutive case series study examining the safety of IDOFORM®Travel in patients with a confirmed diagnosis of HIV infection and continuous cART treatment >4 years and concurrent HIV (ribonucleic acid) RNA <50 copies/mL and CD4+ count <400 cells/μL >3.5 years prior to inclusion. There will be no control arm to the intervention. The primary objective is safety assessment. The secondary objective is exploratory. End points at the termination of the intervention will be compared to the parameters at inclusion. (See chart below.)

Study Period	Estimated date of first patient enrolled:	01.12.2015
	Anticipated recruitment period:	18 months
	Estimated date of last patient completed:	30.11.2017
Treatment Duration:	8 weeks	
Follow-up:	Follow-up terminated at termination of treatment	

In a subsidiary cross sectional case control study, the patients included in the intervention will at baseline (week 0) be compared with individuals with chronic HIV infection and continuous cART >4 years and concurrent HIV RNA <50 copies/mL and CD4+ count >600 cells/μL >3.5 years prior to inclusion, and with

HIV uninfected individuals, both control groups matched to cases with regards to gender, ethnicity, age, and comorbidity

Project scheme

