7.2 Safety and Tolerability Assessments

Safety will be monitored by the assessments described below as well as the collection of AEs at every visit. Significant findings that are present prior to the signing of informed consent must be included in the relevant medical history/ current medical condition page of the CRF. For details on AE collection and reporting, refer to Section 8.3.

For the assessment schedule refer to Flow chart in Section 6.1.

At inclusion (week 0) and at interventional product stop (week 8) patients will go through physical examination, vital signs evaluation, and blood samples for medical biochemistry analysis.

- Physical examination will include an examination of general appearance, skin, eyes, heart, abdomen, and peripheral lymph nodes.
- Vital signs include body temperature, blood pressure, pulse, and respiratory rate. Seated blood pressure and respiratory rate assessments will be performed after 2 min seated rest in a chair next to colonoscopy bench prior to colonoscopy.
- Medical biochemistry analysis consists of: Hemoglobin, white blood cells count, Thrombocytes, CRP, sodium, potassium, creatinine, ALAT, Bilirubin, Albumin, Amylase, and CK.

At weeks 1, 3, 5, and 7, participants will be telephoned and asked for side effects or adverse symptoms. Symptoms will be categorized as:

- General (fever, wellbeing/sense of illness, fatigue).
- Circulatory (palpitations, thoracic pain/discomfort, cold/painful extremities)
- Respiratory (shortness of breath, coughing, bronchial discharge)
- Dermal (rash, pruritus).
- Gastrointestinal (diarrhea, bloating, nausea, abdominal pain/discomfort).
- Other.

In case of side effects or adverse symptoms, participants will be called in for a visit for physical examination and vital signs and evaluation of need for discontinuation of study.

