8.2 Time Period for Reporting AE and SAE

For each patient the standard time period for collecting and recording AE and SAEs will begin at start of study treatment (week 0) and will continue 14 days following the last dose of study treatment, for each patient.

During the course of the study all AEs and SAEs will be proactively followed up for each patient; events should be followed up to resolution, unless the event is considered by the investigator to be unlikely to resolve due to the underlying disease. Every effort should be made to obtain a resolution for all events, even if the events continue after discontinuation/study completion.

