10 STATISTICAL METHODS AND DATA ANALYSIS

10.1 Determination of Sample Size

The study probiotic (IDOFORM®Travel) has previously not been tested in HIV-infected patients. Other probiotics have been well tolerated in other samples of HIV-infected patients, but has not been tested in INR patients.(58-60) We expect the probiotic to have few side effects and adverse events occurring at a low frequency. The study design for assessment of the primary objective is an uncontrolled intervention for detection of adverse events occurring at a frequency and with a severity that disqualify further efficacy studies of the investigational product.

There are no published data providing an expected frequency or variability of adverse events that could be applied in power or sample size calculations for the primary objective of this study. For the safety study, 20 patients will be observed for serious adverse events (SAE) for 8 weeks. If we observe 0/20 adverse events then we can be 95% certain that the true population proportion of SAE in 2 weeks fall within the range (0%, 17%). If we observe 1/20 adverse events then we can be 95% certain that the true population proportion of SAE in 8 weeks fall within the range (0.1%, 25%). Here the confidence intervals have been calculated using the Clopper-Pearson method.(67)

The secondary objectives of the study are exploratory. There are no relevant published data that can provide expected efficacy size or variability. Sample size calculations for the secondary objectives are therefore not feasible.

The sample size in this study is also influence by queries in our HIV database on number of patients eligible for inclusion and by available resources at the departments participating in the study.

Expert statistician at Regional Research Support at OUH has been consulted.

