10.4 Statistical Analysis

Non-parametrical statistics will be applied for all analyses, two-sided tests only. Level of statistical significance defined as $p < 0.05$. Patients with missing values will be excluded from analysis of the parameter where value is missing. This study does not have any additional separate statistical analysis plan.

Primary endpoints: (see section 2.1)

i) Adverse events:

- a. Descriptive presentation of frequencies concurrent to study treatment. No comparative statistical analysis.

ii) Δ plasma HIV RNA load:

- a. Δ defined by changes between end of study (week 8) and baseline (week 0).
- b. Assessed by routine HIV RNA quantification at Dep. of Medical Microbiology, OUH.
- c. H_0 : Eight weeks treatment with probiotics does not change HIV RNA load in INR cART-treated chronic HIV-infected patients.
- d. Analyzed by Wilcoxon signed-rank test.

iii) Δ blood CD4 count:

- a. Δ defined by changes between end of study (week 8) and baseline (week 0).
- b. Assessed by routine CD4 cell quantification at Dep. of Immunology, OUH.
- c. H_0 : Eight weeks treatment with probiotics does not change blood CD4 cell count in INR cART-treated chronic HIV-infected patients.
- d. Analyzed by Wilcoxon signed-rank test.

Secondary endpoints: (see section 2.2)

The statistical analysis strategy is described below. As the efficacy assessments of this study are of exploratory nature, the exact parameters assessed and variable to be analyzed are difficult to predict. The conductance of the statistics may diverge from the planned analyses.

- Alterations are defined by:
 - Changes in *variable* between end of study (week 8) and baseline (week 0) in INR cART-treated chronic HIV-infected patients.

or

- Differences in *variable* between INR cART-treated chronic HIV-infected patients (week 0) (cases) and cART-treated immunological responding chronic HIV-infected patients (controls) and HIV negative subjects (healthy controls).
- Null hypothesis (H_0) will be formulated as:
 - H_{0-1} : Eight weeks treatment with probiotics does not alter the *variable* in INR cART-treated chronic HIV-infected patients.

or

- H_{0-2} : INR cART-treated chronic HIV-infected patients (week 0) (cases), cART-treated immunological responding chronic HIV-infected patients (controls) and HIV negative subjects (healthy controls) have equal *variable*.
- Statistical tests will consist of:

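### Section 3 (follow-up ends at week 8) and section 6.2.5 (AE call at week 12) do not match the week 10 safety window fixed in 8.2, and the analysis text in 10.1 and 10.4(i) is not tied to that window

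*Combined protocol and SAP*

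**What the plan says.** Section 8.2 is the only place that defines when AE and SAE collection starts and stops. It starts at week 0 and "will continue 14 days following the last dose of study treatment, for each patient". The synopsis agrees: "One follow-up consultation 2 weeks after completed therapy". So does the flow chart in 6.1. Its follow-up column stands at week 10, is marked as a telephone interview for the intervention patients ("INR patients/intervention study only"), and has the adverse-events row ticked. Section 7.2 makes that chart the reference: "For the assessment schedule refer to Flow chart in Section 6.1".

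Two other lines of current text differ. The study-period table in section 3 gives "Follow-up terminated at termination of treatment". Section 6.2.5 gives "Week 12: Telephone interview recording adverse events".

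On analysis, section 10.1 states that "20 patients will be observed for serious adverse events (SAE) for 8 weeks". It then attaches a 2-week period to the interval for 0/20 and an 8-week period to the interval for 1/20. Section 10.4(i) specifies the primary AE analysis as "Descriptive presentation of frequencies concurrent to study treatment", with no comparative test, and does not say how that period relates to 8.2. Section 10.4 also says that there is no separate statistical analysis plan, so no other document settles the point.

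**The concern.** The product contains live bacteria. Section 1.2 justifies a phase I safety study by reported septicaemia in people with compromised immunity. An infection that appears shortly after the last dose bears directly on the primary objective. Under 5.3 the last dose is taken on the day of the second colonoscopy, so late procedural complications fall in the same fortnight.

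Two things are at stake. The first is conduct: staff who follow section 3 would make no call after treatment, and staff who follow 6.2.5 would call two weeks after the 8.2 window has closed. The second is reporting: events collected in the 14 post-dose days have no stated place in the primary AE table. Section 10.3 allows the analysis plan to be amended up to database lock, and the study is open label, so the period is better fixed before the events are known.

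**Working it through.** **1. The plan's own figures.** Section 10.1 gives two-sided 95% Clopper-Pearson intervals for n = 20.
- 0/20: the upper limit solves (1 − p)^20 = 0.025, so p = 1 − 0.025^(1/20) = 16.84%. Stated: 0% to 17%.
- 1/20: the lower limit solves 1 − (1 − p)^20 = 0.025, so p = 1 − 0.975^(1/20) = 0.13%. The upper limit solves (1 − p)^20 + 20p(1 − p)^19 = 0.025, so p = 24.87%. Stated: 0.1% to 25%.

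Both reproduce. The limits depend only on the count and n, so the 2-week label on the first is an error of wording and the number is right.

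**2. Timeline.** The last dose is at the week 8 colonoscopy (5.3 and 6.1).

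| Place | What it fixes | Week |
|---|---|---|
| 8.2 | end of AE/SAE collection, last dose + 14 days | 8 + 2 = 10 |
| Synopsis | follow-up contact, 2 weeks after therapy | 8 + 2 = 10 |
| 6.1 flow chart | follow-up telephone contact, AEs ticked | 10 |
| Section 3 table | end of follow-up in general | 8 |
| 6.2.5 | date of the AE telephone call | 12 |

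Three places agree on week 10. Section 3 and 6.2.5 are the outliers.

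**3. Gaps between scheduled contacts.** Contacts at weeks 0, 1, 3, 5, 7 and 8 give gaps of 7, 14, 14, 14 and 7 days. The next gap is (10 − 8) × 7 = 14 days under the flow chart and (12 − 8) × 7 = 28 days under 6.2.5. Under section 3 there is no further contact.

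**4. Share of the window.** Nominally 8 × 7 + 14 = 70 days, and 14/70 = 20.0%. Section 5.3 puts the first dose two days after the first colonoscopy. Counted from the first dose, with the second colonoscopy on day 56, 57 or 58, the window is 69, 70 or 71 days and the share 20.3%, 20.0% or 19.7%. For 20 completers the tail is 20 × 14 = 280 of 20 × 70 = 1,400 patient-days. These are shares of calendar time; they do not count events.

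**5. What the choice of period could do to the count.** The documents give no AE rate, so this step rests on an assumed constant hazard: p10 = 1 − (1 − p8)^(10/8).

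| Assumed 8-week proportion | 10-week proportion | Expected patients of 20, 8 weeks → 10 weeks |
|---|---|---|
| 5% | 6.2% | 1.00 → 1.24 |
| 10% | 12.3% | 2.00 → 2.47 |
| 20% | 24.3% | 4.00 → 4.87 |

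The difference is about 0.2 to 0.9 patients. If one patient's first SAE fell in the post-dose days, counting it or not would move the reported interval between 0% to 16.8% and 0.13% to 24.9%.

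**The case against.** Several stronger readings are tempting, and the documents do not support them.

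A reader might infer that the protocol has three competing end points for AE collection. It has one, in 8.2. The section 3 entry is a general follow-up line in an overview table and schedules nothing. The 6.2.5 entry dates a call, and a call at week 12 can still ask about events up to week 10.

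A reader might infer that 10.4(i) leaves the AE period entirely open. It does not: its wording reads most plainly as on-treatment events, which fits the 8 weeks in 10.1. An on-treatment table beside a longer collection window is a legitimate choice, so widening the table is partly a preference. What stands is narrower: the term is not defined or linked to 8.2, so collected post-dose events have no stated place.

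A reader might take the 2 weeks in 10.1 for a separate post-treatment period. The sentences on either side both say 8 weeks, so it is better read as a slip.

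A reader might fear that a serious late infection would be missed. Patients are told to contact the investigator at once about symptoms they perceive as serious (section 8). SAEs go to the sponsor within 24 hours of the site learning of them (8.4.1), and events are followed to resolution even after study completion (8.2). Onset dates are recorded (8.3), and the study report discusses the events of the study (8.4.4). These safeguards leave mainly the non-serious events that a patient mentions only when asked.

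**Conclusion.** The point holds as an internal inconsistency that should be fixed, with modest effect. By the protocol's own safety schedule, the section 3 follow-up line and the 6.2.5 call date are wrong, and the 2-week label in 10.1 does not match the stated observation period. The practical loss is recall of non-serious events over 28 days instead of 14 if 6.2.5 is followed, or no scheduled post-treatment call if section 3 is followed. If staff follow the flow chart, neither loss arises. For analysis, 14 of 70 collection days lack a defined place in the primary AE table. Because that analysis is descriptive, no test, sample size or interval limit for a given count is affected.

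Confidence is high on the mismatch of dates and lower on the consequence for the AE table, which depends on an event rate that the documents do not give. The patient-day figures assume 20 completers.

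**What to change.** - **6.2.5:** move the telephone interview to week 10, 14 days after the last dose.
- **Section 3 table:** replace the follow-up line with one contact two weeks after the end of treatment.
- **10.1:** correct the 2-week label on the 0/20 interval to 8 weeks. If the 8.2 window is adopted for the SAE proportion, use that window for both intervals.
- **10.4(i):** report AEs over the window as 8.2 defines it, week 0 to last dose + 14 days, with on-treatment and post-dose events in separate columns. This keeps the on-treatment table and stops post-dose events from dropping out. Keep the week 0 start and do not replace it with the first dose: the flow chart also marks AEs at baseline, and 5.3 puts the first dose two days later.

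The cost is a wording amendment to four sections, with the approvals that 11.3 requires unless a change counts as administrative. No contact is added, because the week 10 call is already in the flow chart. The sample size and the exact limits for a given count stay as they are.
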